A stepped wedge cluster-randomized trial design will be used to implement the program and to evaluate the effectiveness of Consultagene (primary outcome) in providing genomic care to newborn infants in the RGV and El Paso. The Consultagene platform will be implemented in nine under-resourced NICUs, matched into cohorts based on size (number of beds), and rural/urban status. Based on those characteristics, we will have cohort triads (three NICUs each) which will be simultaneously randomized to the time at which the intervention is implemented.

Inclusion Criteria:

Inclusion criteria: Undiagnosed infants from 0-90 days of age, with a diverse group of phenotypes and strongly suspected to have genetic disorders will be recruited. Samples from biological parents will be obtained whenever available.

Clinicians will be included for interviews who use the Consultagene portal for the MAGNET study.

Exclusion Criteria:

Exclusion criteria include: (1) abnormal noninvasive prenatal testing (NIPT) suggesting chromosomal abnormality; (2) abnormal amniocentesis results, (3) abnormal newborn screening indicating an inborn error of metabolism; (4) abnormal FISH results for aneuploidy (trisomy 18, 13, or monosomy X); (5) Down syndrome; (6) dysmorphic features in the absence of other congenital anomalies; (7) isolated birth defects such as myelomeningocele, cleft lip/palate, cardiac septal defects, isolated congenital diaphragmatic hernia, etc.; (8) birth defects due to known teratogens i.e., alcohol, Isotretinoin, etc.; (9) multiple congenital anomalies associated with maternal diabetes; (10) VACTERL association; and (11) hemodynamically unstable newborns needing transport for higher level of care.

F2. Procedure

We will execute broad reliance agreements and contracts with the NICUs participating in the study after IRB approval. Baylor IRB will serve as the IRB of record for all participating sites. SMART IRB agreement will be used as the basis for reliance. An amendment will be submitted to add each participating site after the reliance agreements are established and before work commences at each site. BCM staff will conduct the research on sites.

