How many subjects (or specimens, or charts) will be used in this study?

Local: 410 Worldwide: 410

Please indicate why you chose the sample size proposed:

Primary Outcome Power Calculation: One of the relevant indicators of the clinical impact is percentage of babies who need genetic screening getting diagnosis. Based on the current published estimates, we anticipate that about 10% of babies at NICU will need genetic screening, and 60% of those babies will likely need to be evaluated by genomics. Currently, none of the 9 participating clinics have performed any WGS or RNA sequencing (baseline). We estimate that about 1/10 of babies who need screening get genetic diagnoses based on the use of other diagnostic methods such as karyotype and chromosomal microarray analysis available to the neonatologists. After the program of genetic screening or Consultagene platform is established and implemented, we expect that all babies who need genetic screening (10/10) or need further genomics evaluation (~6/10) (60%) will receive it. And about 50% of those getting genomics evaluation will get a diagnosis, i.e., 30% of babies who need genetic screening will get a diagnosis.

We do not have prior data on intra-class correlation for NICUs, but we expect it to be large. Specifically, we use different sizes of the cluster (4, 5, 6) i.e. number of babies per NICU requiring genetic screening from whom data will be collected in each time step. Additionally, difference of the correlation values are employed (0.5, 0.6, 0.7). As the intervention effect is anticipated to be large (change from 10% to 30%), we have very high power to detect this change (range from 0.8585 to 99.98).

We will survey 1 caregiver per newborn (n=200).

We will survey each clinician who makes a referral through the Consultagene platform at the time of their first referral (baseline). We will administer clinician followup surveys on an annual basis. Clinician qualitative interviews. About 10 clinicians will be interviewed ~12 months after implementation; all clinicians who make a referral will be invited to participate. Interviews will focus on barriers and facilitators to using the Consultagene platform, satisfaction with and suggested improvements, and perceived fidelity to the intervention.

G2. Data Analysis

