Provide a description of your plan for data analysis. State the types of comparisons you plan (e.g. comparison of means, comparison of proportions, regressions, analysis of variance). Which is the PRIMARY comparison/analysis? How will the analyses proposed relate to the primary purposes of your study?

Primary outcome: Descriptive statistics (proportion and 95% CI) will be presented for each NICU and for all NICUs at each time point. Approximately 40 babies will be recruited per year over 5 years. Cluster or NICU effect will be taken into account when calculating overall data (proportion and 95% confidence intervals). To compare changes before and after intervention (the percent of babies with a diagnosis based on genetic evaluation over the total number of babies suspected to have a genetic diagnosis), mixed-effects model will be used to take into account both time effect and clustering (NICU) effect.

Secondary outcomes: Descriptive statistics (proportion and 95% CI, mean, standard deviation, median, range) of all studied variables collected in caregiver surveys will be examined. Descriptive data will be presented for each NICU and for all NICUs at each time point.

Clinical Outcomes: We will calculate descriptive statistics on patient clinical presentations, such as HPO terms and clinical diagnoses, to characterize the clinical presentation of the patient population, as well as on institutional features of the NICU, such as care level and geographic location, to characterize features of the care setting. Additionally, we will calculate descriptive statistics on clinically relevant laboratory outcomes, such as the turnaround time and outcome (diagnostic versus non-diagnostic) of each test in the multi-omics pipeline and the combined analyses for a particular patient. We will use logistic regression analysis to calculate the odds of WGS diagnosis based on clinical characteristics.

Section H: Potential Risks/Discomforts

H1. Potential Risks/Discomforts

Describe and assess any potential risks/discomforts; (physical, psychological, social, legal, or other) and assess the likelihood and seriousness of such risks:

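### Section F1, read plainly, randomises whole triads of like NICUs to a start time; it should state that NICUs are randomised within each triad

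*Protocol*

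**What the plan says.** Section F1 (Design) announces a stepped-wedge cluster-randomised trial, with the platform "implemented in nine under-resourced NICUs, matched into cohorts based on size (number of beds), and rural/urban status". It continues: "Based on those characteristics, we will have cohort triads (three NICUs each"), and these are the units "cohort triads (three NICUs each) which will be simultaneously randomized to the time at which the intervention is implemented".

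Section G1 (Sample Size) takes cluster sizes of 4, 5 and 6, defined as the "number of babies per NICU requiring genetic screening from whom data will be collected in each time step", with correlations of 0.5, 0.6 and 0.7 and a change from 10% to 30%. It concludes: "we have very high power to detect this change (range from 0.8585 to 99.98"). It gives no number of steps or periods.

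For the primary comparison, section G2 (Data Analysis) says a "mixed-effects model will be used to take into account both time effect and clustering (NICU) effect".

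**The concern.** In the F1 sentence the relative clause attaches to the triads, and there is one implementation time for each. Followed literally, it gives an allocation list in which three like NICUs always start together. Start time is then tied to NICU size and rural/urban type, and the trial randomises three units rather than nine NICUs in three matched sets.

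The G2 model has a time effect common to all NICUs and an effect for each NICU. Neither absorbs a change over time shared only by NICUs of one type, such as a shift in referral practice among the larger urban units. If such a change falls near the step at which that type crosses over, part of it is counted as intervention effect, and the standard error does not allow for it. When the NICUs of each triad are spread over the steps, the same change affects early and late starters of that type alike and cancels.

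The allocation cannot be redone once sites have crossed over, so the sentence needs to be right before the list is drawn.

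**Working it through.** **Inputs from the protocol.** Nine NICUs in three triads (F1); 4 to 6 babies per NICU and time step, ICC 0.5 to 0.7, 10% to 30% (G1); time and NICU effects (G2).

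**Assumptions.** Two-sided 5% level; total variance 0.1 × 0.9 = 0.09, split by the ICC; one baseline period plus three steps of three NICUs, so T = 4 periods. The number of steps is inferred because it reproduces the lower stated power.

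**1. The plan's own figure.** For the standard stepped-wedge model with a NICU random intercept, I = 9. The treatment-indicator sums are U = 18, W = 126 (squared period totals) and V = 42 (squared NICU totals). At 4 babies and ICC 0.5, τ² = 0.045 and σ² = 0.045/4 = 0.01125.

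Var = Iσ²(σ² + Tτ²) / [(IU − W)σ² + (U² + ITU − TW − IV)τ²]
= 9 × 0.01125 × 0.19125 / (36 × 0.01125 + 90 × 0.045)
= 0.019364 / 4.455 = 0.004347, so SE = 0.0659.

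Power = Φ(0.20/0.0659 − 1.96) = 0.8585, the stated lower figure to four decimals. The top of the stated grid (6 babies, ICC 0.7) gives 0.9973, not the stated 99.98 (read as 0.9998), so the layout is only partly confirmed. Both figures are the same whichever unit is randomised, because three NICUs cross at each step either way.

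**2. Number of allocations.** Whole triads: 3! = 6. Within triads: (3!)³ = 216.

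**3. What can be separated.** Give each triad its own free effect in each period (12 columns) and add the treatment column, 13 in all. With whole triads, the three NICUs of a triad always share the same treatment status, so the treatment column is a sum of the other columns. The rank is 12 of 13 in all 6 allocations. Within triads it is 13 of 13 in all 216.

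A more restricted pattern is different. With common periods, triad intercepts and triad-specific linear trends, the whole-triad design has full rank (9 of 9) in all 6 allocations. Power is then 0.832 against 0.858 (4 babies, ICC 0.5), or 0.996 against 0.997 (6 babies, ICC 0.7).

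**4. Bias under the G2 model, assumed drift.** One NICU type drifts linearly by 15 points over the trial.
- Whole triads, 4 babies, ICC 0.5: the estimate shifts by −1.5, −0.5 or +1.9 points, depending on that type's start time (mean zero over the 6 allocations).
- Whole triads, over the G1 grid: −1.5 to +2.0 points. A 5-point drift gives a third of this, at most 0.7.
- Within triads: 0 in every allocation.

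**5. Precision and error rate with whole triads, assumed shared variation.** Let all NICUs of a triad share a random period deviation with standard deviation s. At 4 babies and ICC 0.5 the true variance is 0.004347 + 1.122 s², where 1.122 is the sum of squared triad-by-period weights in the estimate.

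| s (points) | True SE | Power | Type I error, G2 model |
|---|---|---|---|
| 0 | 0.0659 | 0.858 | about 5% |
| 1 | 0.0668 | 0.850 | about 5.3% |
| 3 | 0.0732 | 0.780 | about 7% |
| 5 | 0.0846 | 0.657 | about 10% |

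The 5.3% is closed-form with known variances: 1.96 × 0.0659/0.0668 = 1.93. The last two rates come from simulation (12,000 replicates, Gaussian NICU-period means, REML, t with 23 degrees of freedom), which gave 7.0% and 10.3%. At 6 babies and ICC 0.7, power falls from 0.997 to 0.964 (s = 3) and 0.829 (s = 5).

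**6. The same variation within triads.** The weights of each triad sum to zero in every period, so shared deviations cancel from the estimate. The unchanged G2 model becomes somewhat conservative. At 4 babies and ICC 0.5, type I error is 4.5% at s = 3 and 3.5% at s = 5. Simulated power is 0.813 and 0.790, against 0.827 at s = 0 on the same t reference.

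**The case against.** **The text may simply be loose.** Matching like NICUs makes most sense if they are then split across start times, and the word for simultaneous may mean only that all triads are randomised at one sitting. This stands as far as intent goes. A reader might infer that the sponsor has chosen to start like NICUs together, and the protocol does not establish that. But nothing in it says that NICUs of one triad start at different times, and the list will be drawn from the sentence as written. A further reading, that the cohorts were made alike to one another, is strained, since the triads are formed from the matching characteristics themselves.

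**Analysis could rescue the whole-triad design.** In part it could. A reader might infer from the rank result that no model term helps. That is wrong: triad-specific linear trends remove the linear drift of step 4 completely at a small cost in power, and, with known variances, a random triad-by-period term gives an honest standard error (0.0731 at s = 3) without recovering the lost power. The rank result covers only unrestricted type-by-period effects.

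**The harm rests on assumed inputs.** This stands. The protocol gives no type-specific trend or triad-by-period variation. A 15-point drift is large beside a usual-care yield of about 10%. At s = 1 the loss is slight, and with no such variation the two allocations perform alike.

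**The step count and extra model terms are detail.** This largely stands. Nine NICUs in three triads suggest three steps on either reading, and further model terms can be left to the SAP.

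**Conclusion.** The point holds as a defect of wording with a design consequence. As written, F1 randomises three blocks of like NICUs, with 6 allocations rather than 216, and unrestricted type-by-period changes cannot then be separated from the intervention.

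The size is conditional on assumed variation and on an inferred layout of three steps and four periods, which matches the lower stated power but not the upper. Bias is small: at most about 2 points of 20 for a 15-point drift, and zero on average over allocations. The larger risk is to power and error rate. At 4 babies and ICC 0.5, power of 0.86 becomes 0.85, 0.78 or 0.66 at a shared SD of 1, 3 or 5 points, and type I error rises from 5% to about 5.3%, 7% or 10%.

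A reader might infer that the primary result would be seriously biased or beyond repair by modelling. The figures do not support that. The case for change is that the weaker allocation gains nothing in nominal power, cannot be undone after roll-out, and is avoided by one sentence.

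**What to change.** Replace the F1 sentence with: *Within each triad of NICUs matched on number of beds and rural/urban status, the three NICUs will be randomised to the three implementation times, so that one NICU from each triad crosses over at each step.* This also states the number of steps, which the sponsor should confirm, since three is inferred here.

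The cost is one sentence and the allocation list. It needs no added sites or babies, and nominal power is unchanged (0.8585 in the lowest scenario). The small downside is that each onboarding wave mixes NICU types. Any effect on the calendar cannot be checked, as the protocol gives no step dates. If within-triad randomisation was already intended, only the wording changes.

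A triad-specific period term in the mixed model is optional and can be left to the SAP. In the simulations it returned type I error to about 5% and added 0 to 3 points of power where such variation exists. It uses six degrees of freedom (23 to 17), and power at 4 babies and ICC 0.5 with no such variation was 0.819 against 0.827.

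### The stated low power of 0.8585 is reproduced with the 10% rate's variance for every infant; counting the planned 30% rate as well gives about 0.65 on the same layout

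*Protocol*

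**What the plan says.** Section G1 sets the control rate with "We estimate that about 1/10 of babies who need screening get genetic diagnoses" and the intervention rate with "30% of babies who need genetic screening will get a diagnosis". For the grid it says "we use different sizes of the cluster (4, 5, 6", defined as the "number of babies per NICU requiring genetic screening from whom data will be collected in each time step". For the ICC, "difference of the correlation values are employed (0.5, 0.6, 0.7". It concludes "we have very high power to detect this change (range from 0.8585 to 99.98".

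Section F1 describes nine NICUs in "cohort triads (three NICUs each) which will be simultaneously randomized to the time at which the intervention is implemented". Section G2 says a "mixed-effects model will be used to take into account both time effect and clustering (NICU) effect", and plans about 40 babies a year over 5 years, or about 200.

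G1 gives no formula, variance, alpha or number of periods.

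**The concern.** A binary outcome has variance p(1 − p), which is 0.09 at 10% and 0.21 at 30%. In a stepped wedge with one baseline period and three steps, half of the NICU-periods are under the intervention. If the power calculation gives all of them the 10% variance, it contradicts the effect it is meant to detect and understates the standard error.

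This is the only power justification the protocol gives for its primary comparison. A reader of G1 would conclude that even the least favourable scenario has about 86% power.

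**Working it through.** **Inputs.** Difference 0.30 − 0.10 = 0.20 (G1). I = 9 NICUs in three triads (F1). m = 4, 5 or 6 per NICU per step and ICC = 0.5, 0.6 or 0.7 (G1). Model with time and NICU effects (G2). Assumed, because not stated: T = 4 periods (one baseline and three steps), two-sided alpha 0.05, normal approximation.

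**Formula (Hussey-Hughes).** Split the total variance v into τ² = ICC × v between NICUs and σ² = (1 − ICC) × v / m for a NICU-period mean. Then

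Var = I σ²(σ² + Tτ²) / [(IU − W)σ² + (U² + ITU − TW − IV)τ²]

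For this layout:
- U (intervention NICU-periods) = 3 × (3 + 2 + 1) = 18, out of 36
- W (sum of squared period totals) = 0 + 9 + 36 + 81 = 126
- V (sum of squared NICU totals) = 3 × (9 + 4 + 1) = 42
- IU − W = 162 − 126 = 36
- U² + ITU − TW − IV = 324 + 648 − 504 − 378 = 90

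Power = Φ(0.20/SE − 1.96).

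**Step 1: reproduce the stated low end (m = 4, ICC 0.5, v = 0.09).** σ² = 0.045/4 = 0.01125 and τ² = 0.045. Var = 9 × 0.01125 × (0.01125 + 0.18) / (36 × 0.01125 + 90 × 0.045) = 0.019364/4.455 = 0.004347, so SE = 0.0659. Power = Φ(3.034 − 1.960) = **0.8585**, matching G1 to four decimals at the lowest cell of the grid.

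**Step 2: same layout with both rates.** Mean variance v = (0.09 + 0.21)/2 = 0.15. Var scales by 0.15/0.09 to 0.007244, so SE = 0.0851. Power = Φ(2.350 − 1.960) = **0.652**.

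**Step 3: the full grid, four periods.**

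| m | v = 0.09, ICC 0.5 / 0.6 / 0.7 | v = 0.15, ICC 0.5 / 0.6 / 0.7 |
|---|---|---|
| 4 | 0.859 / 0.921 / 0.973 | 0.652 / 0.743 / 0.852 |
| 5 | 0.922 / 0.964 / 0.991 | 0.745 / 0.830 / 0.918 |
| 6 | 0.959 / 0.984 / 0.997 | 0.817 / 0.890 / 0.956 |

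With both rates, three of nine cells are below 0.80.

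**Step 4: the upper end.** With v = 0.09 the listed sizes reach at most 0.9973 (m = 6, ICC 0.7). The printed 99.98, read as 0.9998, appears on the same basis at m = 8, ICC 0.7: σ² = 0.027/8 = 0.003375, τ² = 0.063, SE = 0.0366, power 0.9998. G1 does not list m = 8. This supports the inferred basis and suggests, without proving, that the top figure came from a wider grid.

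**Step 5: sensitivity of the low corner (m = 4, ICC 0.5, four periods).**
- Pooled variance 0.2 × 0.8 = 0.16: 0.624.
- Residual variances 0.045 (control) and 0.105 (intervention) with one between-NICU variance of 0.075: 0.680. The ICC of 0.5 is then only an average (0.075/0.120 = 0.625 and 0.075/0.180 = 0.417).
- Between-NICU variance also rising with the rate, ICC 0.5 in both conditions: 0.588, or 0.576 when the analysis uses equal-variance weights.
- Critical value from the null variance 0.09, alternative from 0.15: Φ((0.20 − 1.96 × 0.0659)/0.0851) = 0.797. The other eight cells are then at least 0.863.

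**Step 6: other layouts at the low corner, v = 0.09 / 0.15 / 0.16.**

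| Layout | v = 0.09 | v = 0.15 | v = 0.16 |
|---|---|---|---|
| 5 periods, one per step | 0.890 | 0.695 | 0.667 |
| 6 periods, one per step | 0.908 | 0.721 | 0.694 |
| 6 periods, two per step | 0.970 | 0.846 | 0.822 |
| 7 periods, two per step | 0.983 | 0.886 | 0.865 |
| 8 periods, two per step | 0.989 | 0.909 | 0.891 |

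With the four-period layout this makes 18 combinations of layout and variance. Only four periods with 0.09 gives 0.8585. With v = 0.15, three of nine cells are below 0.80 at five periods and one of nine at six (one period per step).

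**The case against.** The basis is inferred. G1 states no formula, and a statistical analysis plan not seen here may hold the details. That stands as a limit on certainty. Some other settings come close to 0.8585: two periods per step over seven periods with pooled variance gives 0.865, but it needs 9 × 7 × 4 = 252 infants even at m = 4, against about 200 planned. Other near matches drop the time effect that G2 requires, use a one-sided test, or abandon the triads in F1. None is exact.

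The 0.65 is also the least favourable cell. It uses 9 × 4 × 4 = 144 infants. If the 200 planned babies filled the 36 NICU-periods, m would be about 5.6 and power with v = 0.15 would be 0.787, 0.866 and 0.942 for ICC 0.5, 0.6 and 0.7. Whether the 200 includes control-period infants is unclear. It is fair to say that most listed scenarios stay above 0.80. G1's claim, however, covers its whole range, and its low end is the figure shown to be too high.

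The size of the drop depends on convention. Under the most favourable one on the four-period layout (0.797), the overstatement is modest. Finally, a linear model with ICC 0.5 to 0.7 at a 10% rate is a rough approximation, since many NICU rates would lie near 0 or 1. The recomputed values therefore correct G1 on its own terms and are not a definitive power.

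**Conclusion.** The concern holds. The low end of G1's range is matched to four decimals when the 10% rate's variance is applied to every infant, and the upper end fits the same basis at a cluster size G1 does not list. Adding the protocol's own 30% rate lowers the low corner from 0.86 to about 0.65 and puts three of the nine listed scenarios below 0.80. Every convention tried on this layout that uses both rates falls short of 0.8585 (0.58 to 0.80).

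This rests on three inferred inputs: four periods, two-sided 0.05 and variance 0.09. Two data-collection periods per step would bring the low corner back to 0.846 or more with variance 0.15, but that layout does not reproduce the printed figure. Confidence is medium. The mixed units need no inference: 0.8585 is a proportion and 99.98 a percentage.

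**What to change.** Recompute the G1 grid with a variance that reflects both the 10% and the 30% rate. State the formula, period count and alpha, and report one unit for the cluster sizes actually listed. Under the four-period, two-sided 0.05 reading with mean variance, the range would be about 0.65 to 0.96. If the upper figure came from a cluster size outside 4 to 6, list that size or drop the figure. Replace the wording on high power with the corrected range.

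The cost is a wording change to the protocol, with no extra patients and no change to design or analysis. The drawback is a less favourable stated power.

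### The power range in G1 mixes two scales, and very high power does not hold across the listed scenarios once both expected diagnosis rates enter the variance

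*Protocol*

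**What the plan says.** Section F1 sets the design: "A stepped wedge cluster-randomized trial design will be used to implement the program". It continues: "The Consultagene platform will be implemented in nine under-resourced NICUs", and "we will have cohort triads (three NICUs each) which will be simultaneously randomized to the time at which the intervention is implemented".

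Section G1 expects the share of screened babies who receive a diagnosis to rise from 10% to 30%. It admits that there are no prior data on the intra-class correlation and sets out a grid. For cluster size, "we use different sizes of the cluster (4, 5, 6) i.e. number of babies per NICU requiring genetic screening", with the unit given as "from whom data will be collected in each time step". For correlation, "difference of the correlation values are employed (0.5, 0.6, 0.7". It concludes that "we have very high power to detect this change (range from 0.8585 to 99.98".

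On enrolment, section G2 says "Approximately 40 babies will be recruited per year over 5 years", that is 200 infants. G1 surveys one caregiver per newborn, also 200, and gives a total of 410 subjects. G1 does not give the significance level, the number of periods or the outcome variance behind the power figures.

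**The concern.** The printed range cannot be read as it stands, because its ends are on different scales. Reading the second figure as 99.98%, one would expect the nine combinations of cluster size and correlation to span 0.8585 to 0.9998 under a single set of assumptions.

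The larger question is which variance produced the figures. For a binary outcome the variance depends on the rate, and this design expects two quite different rates. If only the lower rate was used, the power is too high everywhere in the grid. This paragraph of G1 is the protocol's only quantitative support for its size, so a reader relying on it would take the worst listed case to be comfortably above 80%.

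**Working it through.** **Inputs.** From F1: I = 9 NICUs in triads, read as three sequences of three. From G1: n = 4, 5 or 6 infants per NICU per time step; ICC ρ = 0.5, 0.6 or 0.7; difference 0.30 − 0.10 = 0.20. Assumed, because not stated: T = 4 periods (a baseline plus three steps) and a two-sided 5% test.

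**Formula** (Hussey–Hughes: fixed period effects, random NICU intercept). With total variance v, let σ² = (1 − ρ)v/n and τ² = ρv. Then

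Var = Iσ²(σ² + Tτ²) / [(IU − W)σ² + (U² + ITU − TW − IV)τ²], and power = Φ(0.20/√Var − 1.96).

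For this layout:
- U = 3 × (3 + 2 + 1) = 18
- W = 0² + 3² + 6² + 9² = 126
- V = 3 × (3² + 2² + 1²) = 42
- IU − W = 162 − 126 = 36
- U² + ITU − TW − IV = 324 + 648 − 504 − 378 = 90

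**Step 1: reproduce the lower end.** Take v = 0.1 × 0.9 = 0.09, n = 4, ρ = 0.5. Then τ² = 0.045 and σ² = 0.045/4 = 0.01125.

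Var = 9 × 0.01125 × (0.01125 + 0.18) / (36 × 0.01125 + 90 × 0.045) = 0.019364/4.455 = 0.0043466. The standard error is 0.06593, the ratio 0.20/0.06593 is 3.0336, and power = Φ(1.0736) = **0.8585**. This is the printed figure.

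**Step 2: the most favourable listed cell in the same model.** Take n = 6, ρ = 0.7. Then τ² = 0.063 and σ² = 0.027/6 = 0.0045.

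Var = 9 × 0.0045 × (0.0045 + 0.252) / (36 × 0.0045 + 90 × 0.063) = 0.010388/5.832 = 0.0017813. The ratio is 4.7388, and power = Φ(2.7788) = **0.9973**, not 0.9998.

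**Step 3: use both expected rates.** The intervention-phase variance is 0.3 × 0.7 = 0.21. In this layout 18 of the 36 NICU-periods are under intervention, so the average is (0.09 + 0.21)/2 = 0.15. Changing v only rescales the standard error, by √(0.15/0.09) = 1.291.

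- n = 4, ρ = 0.5: 3.0336/1.291 = 2.3498, power = Φ(0.3898) = **0.65**
- n = 6, ρ = 0.7: 4.7388/1.291 = 3.6707, power = Φ(1.7107) = **0.96**

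| n | v = 0.09; ICC 0.5 / 0.6 / 0.7 | v = 0.15; ICC 0.5 / 0.6 / 0.7 |
|---|---|---|
| 4 | 0.8585 / 0.9212 / 0.9725 | 0.65 / 0.74 / 0.85 |
| 5 | 0.9223 / 0.9643 / 0.9911 | 0.74 / 0.83 / 0.92 |
| 6 | 0.9586 / 0.9844 / 0.9973 | 0.82 / 0.89 / 0.96 |

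Taking the variance at the mean rate of 20% instead (0.2 × 0.8 = 0.16) gives 0.62 to 0.94.

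**Step 4: infants needed.** With four periods the design has 9 × 4 = 36 NICU-periods, so n = 4, 5, 6 needs 144, 180 and 216 infants. Sizes 4 and 5 fit within 200; size 6 exceeds it by 16 (8%).

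**The case against.** The strongest defence is that the lower end, which decides whether the size is adequate, is exact for a listed scenario needing only 144 infants. The upper end is out by only 0.9998 − 0.9973 = 0.0025. Keeping the 0.09 variance and restricting to cluster sizes that 200 infants can fill still gives 0.8585 to 0.9911. All of that stands. On the upper end alone, this would be a reporting slip, and a reader who infers that the whole range is unrelated to this design goes too far. What the defence does not answer is the variance, because it keeps the 10% rate for infants expected to be diagnosed at 30%.

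A second defence is that the sponsor's model is inferred. That is fair: the variance, alpha and number of periods are all back-calculated. A plain two-proportion calculation ignoring clustering, with 18 × 4 = 72 infants per phase, comes close at 0.8586. However, it ignores the NICU and time effects that G2 puts in the analysis, does not vary with the ICC, and reaches only 0.9617 at n = 6. None of the alternative layouts tried returned both printed ends.

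A reader might also infer that 0.9998 was taken from an unlisted, larger cluster size. The documents do not show this. Size 8 with ICC 0.7 gives 0.9998, but so does size 6 with ICC 0.78, and a transcription error is equally possible. The origin is unknown.

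Nor is 216 against 200 a firm contradiction. With three periods, size 6 needs 9 × 3 × 6 = 162 infants; with five, 270. F1 ties the 40 infants a year to sequencing; if they are intervention-phase infants only, size 6 needs 18 × 6 = 108. The 410 total (200 + 200 + about 10 clinicians) points towards 200 infants in all, but the text does not settle it, and the 40 a year is approximate.

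Finally, the large ICCs might be thought cautious. In this model they are not: power rises with ICC from 0.5 to 0.7. At ICC 0.1 and n = 4 it is 0.69 with variance 0.09 and 0.48 with 0.15.

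**Conclusion.** The concern holds in this form. The range in G1 is wrong as printed: its ends are on different scales, and under the model that returns 0.8585 the listed maximum is 0.9973. The material error is the variance. With an average variance of 0.15 from the protocol's own two rates, the grid gives about 0.65 to 0.96 and three of its nine cells fall below 0.80. All three (n = 4 at ICC 0.5 and 0.6; n = 5 at ICC 0.5) fit within 200 infants under the four-period layout.

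This rests on three sequences, four periods, a two-sided 5% test, a normal approximation, and one averaged variance for both phases. It does not show that the trial is underpowered throughout: with n = 5 and ICC 0.6 or 0.7, power is 0.83 or 0.92. It shows that the blanket claim of very high power is unsupported.

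**What to change.** In G1, restate the power range on one scale, calculated with a variance that reflects both the 10% and the 30% rate. State the variance, alpha and number of periods used, so that the figures can be reproduced. Replace the claim of very high power with wording that matches the result.

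Reconcile cluster size 6 with the roughly 200 planned infants by stating the number of periods and whether the 200 cover both phases. If size 6 then cannot be filled, drop it from the grid.

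The cost is a revised paragraph and a less favourable stated power. No change in enrolment is required.
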